The study participants will be matched with historical nonrandomized controls from each site based on sex (female), pathologic stage, receptor status, grade, and menopausal status from each site. These samples will be obtained from blocks no more than 5 years old. The pre-surgical and post-surgical tissue samples (from the participants and matched controls) will be batched and analyzed concurrently utilizing immunohistochemistry and Nanostring to measure any effects of 9cUAB30 on tumor cell proliferation (Ki67) and activation of RXR downstream pathways (gene expression). Slides will be analyzed via immunohistochemistry at Wisconsin and via Nanostring at UAB per existing protocols.

Seven days after surgery and 4-5 weeks after surgery a follow-up phone call will be performed for safety assessment.

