6.9 Blinding and Unblinding Methods

Not applicable

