10.2 Collection and Handling Procedures

The University of Wisconsin Comprehensive Cancer Center’s (UWCCC) CP Laboratory (Cancer Pharmacology Lab) will serve as the central repository for blood and urine specimens. The University of Alabama at Birmingham (UAB) Tissue Biorepository Laboratory and UWCCC TRIP will serve as the central repositories for tissue specimens. The UWCCC CP Laboratory will prepare sample kits for each

subject enrolled on the study – for both the slides being sent to UAB and UWCCC, and the blood and urine being sent to UWCCC. Each site will receive two kits as they activate the study. The CP lab will send additional kits to the sites as needed based on the rate of accrual.

Each kit will be sent in a box to each site. Each box will contain:

- Styrofoam cooler for blood and urine samples and airbill – which go to UWCCC
- Slide mailers, shipping box and airbill for slides – which go to UWCCC and UAB

The University of Washington will ship 2 kits for the 30 mL peripheral blood to each of the sites prior to start of the trial and then will ship further kits to the sites as needed based on recruitment. The University of Washington will train the sites on packing and shipping the blood. All blood processing and storage during the trial will be performed at the University of Washington and after analysis any remaining specimens will be returned to the Division of Cancer Prevention repository.

10.2.1 Methods for preparing tissue specimens of participants and historical matched controls.

NOTE:

- Unstained sections are to be mounted on charged slides
- Historical matched samples should be prepared at the same time as the participant tissue sample.

From both the participant's and historical matched sample of pre-surgical core biopsy and the definitive surgical resection:

- A pathologist should identify, from each procedure, a FFPE archival block that contains an adequate amount of malignant tumor tissue to support the preparation of 11 slides (1 H&E stained slide, 5 unstained slides of 5 μ m thickness and 5 unstained slides of 10 μ m). If the core biopsy will not support the preparation of 11 slides, 1 H&E stained slide, and 5 unstained slides at 5 μ m will be acceptable.
- Samples that are considered adequate and eligible for analysis:
 - From the core biopsy – contain >20% malignant nuclei
 - From the surgical tumor sample – contain >10% malignant nuclei

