- After notification to the respective laboratory, the slides are to be labeled with the study number – UWI 2015-05-01, the PID # assigned to the participant, followed by a P (for pre-surgical core) or S (for surgical) to denote the time-point, followed by a 10 or a 5 (to denote the thickness of the cut), followed by the # of the cut (to denote the order in which the slides were cut from the block) as follows:
 - Labeling of Pre-Surgical Core Biopsy Slides
 - 1 for H&E staining: PID-P
 - 5 unstained to be cut at 5 microns: PID-P5-1, PID-P5-2, ... PID-P5-5
 - 5 unstained to be cut at 10 microns: PID-P10-6, PID-P10-7, ... PID-P10-10
 - Labeling of Surgical Slides:
 - 1 for H&E staining: PID-S
 - 5 unstained to be cut at 5 microns: PID-S5-1, PID-S5-2, ... PID-S5-5
 - 5 unstained to be cut at 10 microns: PID-S10-6, PID-S10-7, ... PID-S10-10

For historical matched control samples – contact CLO to get the Sample ID (SID)

- Labeling of Historical Matched Pre-Surgical Core Biopsy Slides
 - 1 for H&E staining: SID-HP
 - 5 unstained to be cut at 5 microns: SID-HP5-1, SID-HP5-2, ... SID-HP5-5
 - 5 unstained to be cut at 10 microns: SID-HP10-6, SID-HP10-7, ... SID-HP10-10
- Labeling of Historical Matched Surgical Slides

- 1 for H&E staining: SID-HS
- 5 unstained to be cut at 5 microns: SID-HS5-1, SID-HS5-2, ... SID-HS5-5
- 5 unstained to be cut at 10 microns: SID-HS10-6, SID-HS10-7, ... SID-HS10-10
- Unstained sections are to be prepared as follows for participant's samples as well as historical matched samples, cut and prepared in the order listed, placed on the labeled charged slides, and are NOT to be melted:
 - Core Biopsy
 - 1 H&E stained slide
 - 5 unstained at 5 μ m thickness (mounted on charged slides)
 - 5 unstained at 10 μ m thickness (mounted on charged slides)
 - If core will not support the requested # of slides, prepare only the 5 unstained at 5 μ m thickness and do not prepare the 5 unstained at 10 μ m thickness
 - Surgical Resection
 - 1 H&E stained slide
 - 5 unstained at 5 μ m thickness (mounted on charged slides)
 - 5 unstained at 10 μ m thickness (mounted on charged slides)
 - If core will not support the requested # of slides, prepare only the 5 unstained at 5 μ m thickness and do not prepare the 5 unstained at 10 μ m thickness
- Complete the Slide Submission Form located in the lab manual.

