10.3 Shipping Instructions

All samples will be shipped in compliance with the International Air Transport Association (IATA) Dangerous Goods Regulations.

10.3.1 Methods for shipping of tissue slides:

Maintain at room temperature until the slides are packaged and shipped to UAB and Wisconsin within 24

hours of preparation. Slides should be prepared and shipped Monday – Wednesday. They should not be shipped on a Thursday, Friday, on a holiday, or on the day prior to a holiday.

Unstained slides are to be packaged securely in provided slide holders, and packaged carefully (they should not vibrate in the container) to avoid breakage of the slides.

Although slides from more than one participant are encouraged to be prepared and shipped together, it is critical that slides from different participants be packaged in separate slide holders/mailers to avoid confusion.

Slides are to be shipped via overnight delivery, at room temperature, with the Slide Submission Form(s) (Appendix B), and de-identified copies of the pathology reports (labeled with the PID only) using the provided pre-printed airbill to:

1 H&E stained slide and 5 unstained slides cut at 10 microns:

[name]
[name]
[name]
Birmingham, AL 35249-6832

5 unstained slides cut at 5 microns:

[name]
[name]
WI 53792-5669

Call the CP Lab to inform them of a shipment [contact] or email the CP lab mailing list [contact].

10.3.2. Methods for shipping the plasma and urine pharmacokinetics samples:

Once the participant has completed the study, ship the carton containing the pharmacokinetic samples for one participant to the address below. If multiple participants are completing the study, samples from multiple participants can be combined in one shipment.

[name]
[name]
WI 53792-5669

Call the CP Lab to inform them of a shipment [contact] or email the CP lab mailing list [contact]

Use the express courier service indicated by the shipping label contained in the kit. Closely follow all special shipping instructions outlined in the kit instruction packet.

Ship the PK samples only on Monday, Tuesday or Wednesday to ensure safe arrival during the week. Do

not ship the day before a holiday.

Fill the styrofoam cooler with dry ice and put all of the blood and urine samples into the cooler. Place the cooler into the shipping box in which you received the kit.

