This is a single arm open label pre-surgical “window trial” of the novel rexinoid 9cUAB30. The primary objective is to evaluate whether therapy with 9cUAB30 substantially reduces proliferation in breast cancer cells. To test the hypothesis that proliferation decreases in 9cUAB30 treated cases, we plan to examine Ki67 from newly diagnosed breast cancer patients. For each enrolled participant, we will obtain baseline core biopsy tissue samples and post-treatment definitive surgical tissue samples. To account for potential confounding variability associated within the tumor as a result of core biopsy, we plan to include a matched historical nonrandomized “control” group which will have an initial sample as well as post-surgical sample. This matched group will come from archived tissue samples of core biopsy and definitive surgical tissue samples available at each participating Institution. The primary endpoint will be the absolute change in Ki67 expression in each treated participant and matched “control” pair.

The primary analysis will compare the difference in absolute change in Ki67 between treatment and matched “control” group using a one-tailed paired t-test or Wilcoxon signed-rank test, as appropriate, at a significance level of 0.05. We chose the one-tailed test as we are only interested in detecting the reduction in Ki67 expression level with 9cUAB30 as compared to controls.

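### Prescribed labels on the Ki67 slides show treatment group and time point, and the plan does not require re-coding or a masked reader; a cheap safeguard should be added

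*Combined protocol and SAP*

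**What the plan says.** Section 10.2.1 fixes the label of every slide. Participant slides carry the PID, then P (core biopsy) or S (surgery), then the section thickness: "5 unstained to be cut at 5 microns: PID-S5-1, PID-S5-2". Historical control slides carry a separate SID and an added H: "5 unstained to be cut at 5 microns: SID-HS5-1, SID-HS5-2". Sections 3 and 9.1 tie the 5 micron sections to the Ki67 and caspase 3 assays, and section 10.3.1 sends them to Wisconsin.

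On reading, section 3 says: "Slides will be analyzed via immunohistochemistry at Wisconsin and via Nanostring at UAB per existing protocols". Section 9.2 names the Ki67 antibody but gives no counting rule, region selection or image-analysis method.

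Three provisions come near to masking:
- Participant and control samples "will be batched and analyzed concurrently utilizing immunohistochemistry and Nanostring" (section 3).
- "Historical matched samples should be prepared at the same time as the participant tissue sample" (section 10.2.1).
- Slides travel with "de-identified copies of the pathology reports (labeled with the PID only" (section 10.3.1).

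Section 6.9, on blinding, is entered as not applicable. Section 13.1 describes the trial as single arm and open label.

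The primary analysis (sections 13.1 and 13.4) compares the absolute Ki67 change between participants and matched historical controls with a one-tailed paired t-test or Wilcoxon signed-rank test at 0.05. Section 13.1 explains: "We chose the one-tailed test as we are only interested in detecting the reduction in Ki67 expression level".

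**The concern.** Anyone holding a slide with its site label can tell a treated tumour from a control and a core biopsy from a resection. The expected direction, lower Ki67 after drug, is stated throughout the protocol and is the only direction in which the test can reject.

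If Ki67 depends on human judgement, such as counting nuclei or choosing fields, a reader who knows that a slide is a treated resection may score it a little low. The controls are archival and were not randomised, and they were added so that changes due to the biopsy itself would not be mistaken for a drug effect. A group-dependent reading shift enters that same contrast. Neither matching nor the paired test removes it.

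**Working it through.** **1. Do the provisions mask?**

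| Provision | What it controls | Hides group? |
|---|---|---|
| Concurrent batched analysis (3) | Assay drift between runs | No |
| Control slides cut at the same time (10.2.1) | Section age | No |
| De-identified pathology reports (10.3.1) | Personal identity | No |
| Control slides shipped with the matched participant's (10.3.4) | Logistics | No |
| Labels (10.2.1) | Traceability | No; they show it |

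Sections 3, 9, 10 and 13 contain no re-coding step, random reading order or masked score.

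**2. Which reading errors matter?** Let b(g,t) be the average reading error for group g (T treated, C control) at time point t (P core, S surgery). The bias in the paired difference of changes is

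[b(T,S) − b(T,P)] − [b(C,S) − b(C,P)].

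- An error common to both treated time points cancels.
- An error that depends only on time point also cancels, because [b(S) − b(P)] − [b(S) − b(P)] = 0.
- Only a shift in the core-to-surgery change that differs by group survives. Masking group is therefore the essential step, even if tissue appearance reveals the time point.

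**3. Reproduce the plan's power.** Inputs from section 13.3: SDs of 57.5 and 14.8, correlation 0, mean differences of 29.8 to 44.6, and 28 pairs.

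- SD = √(57.5² + 14.8²) = √3525.29 = 59.4, as stated.
- Effect sizes: 29.8/59.4 = 0.502 and 44.6/59.4 = 0.751, as stated.
- Power = P(T > t(0.95, 27)), with T noncentral t on 27 df, noncentrality d√28, √28 = 5.292 and critical value 1.703. For d = 0.502, 0.626 and 0.751 this gives 0.827, 0.943 and 0.987; the table has 0.82, 0.94 and 0.98.

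The same formula can therefore be used below.

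**4. Illustrate a reading shift.** Assume no drug effect and a surviving shift of d SDs of the paired difference in the direction of benefit. The rejection probability is then the actual type I error.

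| Assumed d | Noncentrality | Type I error, paired t |
|---|---|---|
| 0 | 0 | 0.050 |
| 0.05 | 0.265 | 0.083 |
| 0.07 | 0.370 | 0.100 |
| 0.10 | 0.529 | 0.129 |

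Simulation of the signed-rank test with normal differences gives the same values to two decimals (0.08, 0.10, 0.13). The error reaches 0.10 at d = 0.0704, about one-seventh of the smallest planned effect (0.07/0.502 = 0.14).

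On the planning SD of 59.4 these shifts would be 3.0, 4.2 and 5.9 points, averaged over all 28 pairs. The type I error figures use only d and n, so they do not depend on that SD. The values of d are assumptions; the documents give none.

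**The case against.** - **The labels serve site preparation and shipment.** They do not establish what the reader sees. The laboratory's existing protocols and the lab manual are not in the documents and may already provide re-coding. This stands. It limits the finding to what the protocol requires.
- **The scoring method is not stated.** With automated scoring of whole sections, the label would matter little. This also stands, and is why the fix asks for the method. It does not remove the point, since nothing in the plan excludes human judgement.
- **The shift sizes are invented, and any positive shift inflates a one-sided test.** Correct. The table shows sensitivity; it is not an estimate.
- **Section 6.9.** A reader might infer that it rules out masked reading. The documents do not support that. It sits among the pharmaceutical provisions, between registration and agent disposal, and its entry fits open-label dosing. It is not an error, and it says nothing about tissue.
- **Batching and simultaneous preparation are real safeguards.** They are, against drift. They do not conceal group.

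**Conclusion.** The point holds as a cheap improvement. The protocol prescribes labels that show group and time point on the Ki67 and caspase 3 slides, and it does not require that these be hidden from the reader. A site and laboratory could follow it to the letter and leave the one-tailed, non-randomised primary comparison open to reader bias.

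A reader might go further and infer that scoring will be unmasked, or that the false-positive rate will be 0.13. Neither follows. Masking may exist in laboratory procedures outside the documents. The inflation from 0.05 to about 0.08, 0.10 or 0.13 rests on four assumptions: a person scores slides or selects regions; that person knows the group; the resulting shift differs by group in the core-to-surgery change; and it amounts to 0.05, 0.07 or 0.10 SD. The pathology reports add nothing firm, because the documents do not say whether the reader sees them.

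**What to change.** - **10.2.1:** Keep the site labels for shipment and traceability. Add that, before scoring, existing laboratory staff other than the reader cover the labels on the 5 micron slides with a random code containing no PID, SID, H, P or S, and hold the key.
- **9.2 and 13.4:** State how Ki67 is scored, including how regions are chosen and whether by eye or by image analysis. State that participant and control slides are mixed within batches and read in random order. The reader is masked to group, and to time point as far as tissue appearance allows, and has no access to pathology reports or submission forms. The key is released only after scores are locked.
- **13.4:** Use only scores from these masked batches in the primary analysis.
- **6.9:** No correction is needed; a cross-reference to 9.2 is optional.
- If the laboratory already re-codes slides, say so in 9.2.

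The cost is a code list, over-labelling and some tracking. Section 9.1 also plans a variability study on untreated archival samples before treated cases are analysed. Any matched controls already read there would need a second, masked reading. Core and resection tissue may look different, so the realistic gain is masking of group, which is the part that matters for the bias.

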10.2.2 Methods for drawing and processing the pharmacokinetics of blood

At each pharmacokinetic time point (baseline, 5 minutes post day 1 dose, 2 hours post day 1 dose and Day 15-29 prior to surgery), draw one 3ml green top heparinized tube. Centrifuge the tube for 10 minutes to separate plasma. Divide the plasma into 2 cryovial tubes. Label the 2 cryovial tubes with the labels provided in the kit. Make sure to add the participant number, initials, and date of processing to the labels. Freeze the cryovial tubes at -70/ -80°C, and save for transport to the UWCCC CP Laboratory.

10.2.3 Methods for processing the pharmacokinetics of urine

Request the participant to void and record date and time. Store samples immediately at 4°C. Aliquot approximately 10ml of urine into a falcon tube for urine pharmacokinetics. Freeze urine aliquot within 1-4 hours at -70 / -80°C. Discard any remaining urine.

10.2.4 Methods for processing for whole blood.

30 mL of blood will be collected from participants 6-25 at baseline and on day of surgery (Day 15-29) prior to surgery in green top sodium heparin tubes and shipped directly to the University of Washington. Whole blood will cryopreserved in freezing media (10% dimethylsulfoxide and 90% media which includes 12.5% human serum albumin and RPMI-1640 with L-glutamine and 25 mM HEPES) and stored in liquid nitrogen until use in the assay.

10.3 Shipping Instructions

All samples will be shipped in compliance with the International Air Transport Association (IATA) Dangerous Goods Regulations.

10.3.1 Methods for shipping of tissue slides:

Maintain at room temperature until the slides are packaged and shipped to UAB and Wisconsin within 24

hours of preparation. Slides should be prepared and shipped Monday – Wednesday. They should not be shipped on a Thursday, Friday, on a holiday, or on the day prior to a holiday.

Unstained slides are to be packaged securely in provided slide holders, and packaged carefully (they should not vibrate in the container) to avoid breakage of the slides.

Although slides from more than one participant are encouraged to be prepared and shipped together, it is critical that slides from different participants be packaged in separate slide holders/mailers to avoid confusion.

Slides are to be shipped via overnight delivery, at room temperature, with the Slide Submission Form(s) (Appendix B), and de-identified copies of the pathology reports (labeled with the PID only) using the provided pre-printed airbill to:

1 H&E stained slide and 5 unstained slides cut at 10 microns:

[name]
[name]
[name]
Birmingham, AL 35249-6832

5 unstained slides cut at 5 microns:

[name]
[name]
WI 53792-5669

Call the CP Lab to inform them of a shipment [contact] or email the CP lab mailing list [contact].

10.3.2. Methods for shipping the plasma and urine pharmacokinetics samples:

Once the participant has completed the study, ship the carton containing the pharmacokinetic samples for one participant to the address below. If multiple participants are completing the study, samples from multiple participants can be combined in one shipment.

[name]
[name]
WI 53792-5669

Call the CP Lab to inform them of a shipment [contact] or email the CP lab mailing list [contact]

Use the express courier service indicated by the shipping label contained in the kit. Closely follow all special shipping instructions outlined in the kit instruction packet.

Ship the PK samples only on Monday, Tuesday or Wednesday to ensure safe arrival during the week. Do

not ship the day before a holiday.

Fill the styrofoam cooler with dry ice and put all of the blood and urine samples into the cooler. Place the cooler into the shipping box in which you received the kit.

10.3.3 Method for shipping blood samples for immunology

For the 30 mL of peripheral blood for immune evaluation, blood will be packaged per protocol in the shipping box received in the kit and shipped FED-EX priority overnight for next day delivery. The University of Washington Immune Monitoring Laboratory can receive blood shipped Monday through Thursday except the day prior to a national holiday. Prior to shipment, the Immune Monitoring Laboratory must be contacted (contact [contact] to inform that samples are shipped). Any remaining samples after evaluation for the trial will be returned to the Division of Cancer Prevention repository.

UW IML CITN CENTRAL LAB

Attention: [name]
[name]
[name]
Seattle WA 98109

10.3.4 Sample Shipment Schedule:

Sample Type	Time Point	Lab to send (see address above)	Shipment
Tissue Slides	➤ Baseline ➤ Surgery	UAB Tissue Biorepository Laboratory – Alabama UWCCC CP Lab - Wisconsin	Batch Shipment (Pre-surgical and surgical samples)
Historical Tissue Slides	➤ Baseline ➤ Surgery	UAB Tissue Biorepository Laboratory – Alabama UWCCC CP Lab - Wisconsin	To be sent along with the participant that it matches. Batch shipment
Plasma for PK	➤ Baseline ➤ Surgery	UWCCC CP lab - Wisconsin	Batch Shipment
Urine for PK	➤ Baseline ➤ Surgery	UWCCC CP lab - Wisconsin	Batch Shipment
Blood for immunology	➤ Baseline ➤ Surgery	UW IML CITN CENTRAL LAB - Washington	Same day shipment (ambient)

10.4 BioBanking

Biologic specimens collected during the conduct of each clinical trial that are not used during the course of the study will be considered deliverables under the contract and thus the property of the NCI. At study completion, NCI reserves the option to either retain or relinquish ownership of the unused biologic specimens. If NCI retains ownership of specimens, the Contractor shall collect, verify and transfer the requested biologic specimens from the site to a NCI-specified repository or laboratory at NCI's expense.

11. REPORTING ADVERSE EVENTS

DEFINITION: AE means any untoward medical occurrence associated with the use of a drug in humans, whether or not considered drug related. An AE can therefore be any unfavorable and unintended sign, symptom, or disease temporally associated with participation in a study, whether or not related to that participation. This includes all deaths that occur while a participant is on a study.

Please note that all abnormal clinical laboratory values that are determined to be of clinical significance based on a physician's assessment are to be reported as AEs. Those labs determined to be of no clinical significance or of unknown clinical significance (per the physician's assessment) should not be reported as AEs. Any lab value of unknown clinical significance should continue to be investigated/followed-up further for a final determination, if possible.

A list of AEs that have occurred or might occur can be found in §6.2 Reported Adverse Events and Potential Risks, as well as the Investigator Brochure or package insert.

